Balance Recovery Training for Fall Prevention in Retirement Communities

NCT02551666

October 13, 2015

STUDY PROTOCOL

Objective

The objective of this study was to compare the efficacy of RBT versus Tai Chi performed at, and among residents of, older adult senior housing. This RBT is a form of task-specific, perturbation-based balance training involving trip-like perturbations on a modified treadmill (1, 2). Based on evidence of fall risk reduction among older adults (3) and wide implementation, Tai Chi was chosen as an active control training exercise. Outcome measures included reactive balance tests involving trip-like perturbations on the modified treadmill, and standard clinical tests of balance and mobility. We tested two hypotheses, both of which were motivated by the principle of training specificity. We hypothesized that participants randomized to RBT would show better performance on reactive balance tests compared to participants randomized to Tai Chi. We also hypothesized that participants randomized to Tai Chi would show better performance on clinical tests of balance and mobility compared to participants randomized to RBT.

Design

A two-group pretest-posttest design was used. Participants were allocated to RBT or Tai Chi using a computer-based algorithm to minimize differences in key confounders including age (70-79 or 80 and over), gender (male or female), and baseline reactive balance rating (RBR) score (0-12). The pretest was conducted approximately one week prior to starting the assigned intervention. Repeated posttests were conducted one week, one month, three months, and six months after completing the intervention. In addition, real-world falls were tracked for the six months after completing the intervention.

Methods

Pretests and posttests were identical and included a battery of balance tests. The battery of balance tests included six standard clinical tests of balance and mobility, and a reactive balance test. All tests were performed by an investigator who was blinded to participants' group assignment.

Clinical tests: Six fall-risk relevant tests of balance, mobility, and balance confidence were included along with their standard scoring: timed-up-and-go test (TUG) (4), unipedal stance time (5), maximum step length (6), Berg Balance Scale (7), Performance-Oriented Mobility Assessment (POMA) (8), and Activities-specific Balance Confidence Scale (ABC) (9).

Reactive balance test: Participants stood on a stationary modified treadmill (Freemotion 800, Freemotion Fitness, Logan, UT), and reactive balance was assessed in response to a sudden treadmill belt posterior acceleration (~ 40 msec). A slender, rectangular foam block (4×4 cm cross section) was positioned approximately 3-7 cm in front of the toes to elicit a step over an obstacle, similar to that needed after a trip. Participants wore a fall protection harness, supported by an overhead gantry, to prevent knee or hand contact with the treadmill in the event of an unsuccessful attempt to recover balance. Participants were instructed to, upon treadmill movement, step over the obstacle, prevent a fall into the harness, and re-establish stable walking. Two perturbations were performed at each of three speeds (0.8 mph, 1.6 mph, and 2.4 mph) to provide three levels of difficulty (along with two trials at 0.8 mph in the reverse belt direction to reduce anticipation, but these were not included in characterizing reactive balance).

Interventions: Both RBT and Tai Chi interventions involved twelve 30-minute sessions, scheduled three times per week for four weeks. Participants were required to complete at least nine sessions (75% of the total 12) to be considered to be adherent to the protocol; mean RBT and Tai Chi

attendance was 91% and 94%, respectively. Each RBT session involved one participant at a time, and up to 40 treadmill perturbations with rest breaks every 10 perturbations. Perturbations were similar to those during reactive balance tests, with speed and direction (backward or forward belt movement) pseudorandomized to minimize anticipation, and speeds individualized to each participant's capabilities. Each Tai Chi session was led by an instructor with experience in leading community-based Tai Chi for older adults, used 12 unique sequences from the Yang Short Form, and was conducted in groups of a mean size of 5.3 participants. All testing and intervention sessions were performed on-site at the senior housing facilities.

Falls assessment: The number of all-cause falls and trip-induced falls outside of testing and training were recorded over the six months after the intervention (from week 5 to week 28). Such falls were quantified through telephone calls made every two weeks to each participant. A fall was defined as unintentionally coming to rest on the ground or lower level, not caused by loss of consciousness or overwhelming hazard (10).

REFERENCES

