Balance Recovery Training for Fall Prevention in Retirement Communities

NCT02551666

October 13, 2015

STATISTICAL ANALYSIS PLAN

Baseline-post intervention changes in clinical and reactive balance measures were compared between RBT and Tai Chi groups using a mixed model (SAS PROC MIXED procedure, SAS Institute Inc., Cary NC) that accounted for fixed and random effects, and within-participant correlation. For the clinical tests, fixed effects of intervention (RBT or Tai Chi), time (one week, one month, three months, or six months post-intervention), and intervention*time were included, as well as covariates of baseline (pre-intervention) performance, age, gender, and baseline reactive balance rating score. For the reactive balance measures, fixed effects of intervention, time, speed, and all two-factor interactions were included, along with the same covariates noted above. Hierarchical models were used in analyzing reactive balance measures to account for the two levels of repeated measures (time and speed) and the two replications of each time-speed combination. *A priori* simple effects investigated differences between intervention groups at each time point to address our hypotheses, and the Tukey-Kramer method was used to adjust for Type I error rate, with a significance level of $p \leq .05$. Differences in categorical variables between groups were evaluated using Fisher's Exact Test.

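### Does hypothesis 2 need a new multiplicity rule because it rests on six clinical tests at four visits?

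*Protocol*

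**What the plan says.** The Protocol's Objective describes outcomes in the plural and ranks none of them: "Outcome measures included reactive balance tests involving trip-like perturbations on the modified treadmill, and standard clinical tests of balance and mobility". Its second hypothesis is that "participants randomized to Tai Chi would show better performance on clinical tests of balance and mobility compared to participants randomized to RBT". The clinical tests appear under Methods: "Six fall-risk relevant tests of balance, mobility, and balance confidence were included along with their standard scoring". They are TUG, unipedal stance time, maximum step length, Berg Balance Scale, POMA and ABC. On timing, the Design section says: "Repeated posttests were conducted one week, one month, three months, and six months after completing the intervention".

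The SAP is one paragraph. It specifies a mixed model: "For the clinical tests, fixed effects of intervention (RBT or Tai Chi), time (one week, one month, three months, or six months" post-intervention) and their interaction, plus covariates. It then says that "simple effects investigated differences between intervention groups at each time point to address our hypotheses", and that "the Tukey-Kramer method was used to adjust for Type I error rate", at the .05 level. It does not mention a primary clinical test, a composite, a required number of favourable tests, or the set of comparisons that Tukey-Kramer spans. Neither document calls hypothesis 2 primary or confirmatory.

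**The concern.** A single directional claim is examined through 24 between-group contrasts. Tukey-Kramer works on the means of one fitted model. Test is not a factor in the clinical-test model, so the adjustment cannot act across the six tests.

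Within one test, its effect depends on the family. Applied to the two group means at one visit, it adjusts nothing. Applied to all eight group-by-time means, it is strict.

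If a reader took any one significant test as support for hypothesis 2, the chance of a false claim for Tai Chi could lie anywhere from about 2% to nearly 40%, and the SAP wording would not say which. At stake is how much weight an isolated significant clinical result can bear.

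**Working it through.** The documents state no sample size, power or family-wise error figure, so there is none to reproduce. The check asks what error rate each reading would imply.

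**Inputs from the documents.** Six tests (Protocol, Methods); four post-tests (Protocol, Design); two groups; level .05 (SAP). Contrasts: 6 × 4 = 24. Group-by-time means per test: 2 × 4 = 8. Pairs of these: 8 × 7 / 2 = 28.

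**Assumptions.** No true difference; two-sided tests, so 0.025 in the Tai Chi direction; large sample; exchangeable correlations of 0–0.7 between tests and 0.5–0.7 between visits. A test counts as favourable if any of its four visits is significant for Tai Chi.

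**Critical |z|, by reading of the Tukey-Kramer family**
- Per visit, two means: 1.960, the unadjusted value.
- All 28 pairs: studentized range for 8 means, divided by √2 = 3.031.
- Four between-group contrasts held jointly at 5% per test: 2.442 or 2.377 (between-visit correlation 0.5 or 0.7). This is not a true Tukey-Kramer family, because the method covers all pairwise differences among a set of means. It is shown for comparison only.

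**False support for Tai Chi** (simulation of 24 correlated normal statistics, 400,000 draws per setting)

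| Support rule | Per visit | All 28 pairs | Four contrasts |
|---|---|---|---|
| Any one of six tests | 19.0–38.6% | 1.6–2.7% | 8.5–14.2% |
| At least two of six | 5.4–11.5% | 0.5% or less | 0.9–3.4% |
| All six | 0.8% or less | about 0% | 0.1% or less |

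A second run with 800,000 draws agrees with the ends of the any-one-of-six ranges to within about 0.1 percentage point. The 1.6% is from that run; the first gave 1.7%.

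**Closed-form checks.** Six independent tests at 0.025 give 1 − 0.975^6 = 14.1%, the upper end of the four-contrast column. Twenty-four independent contrasts give 1 − 0.975^24 = 45.5%, the ceiling for the per-visit reading. Over wider correlations (0–0.8 between tests, 0–0.9 between visits), any one of six gives 12–45.5% per visit and 1.0–3.0% for all pairs.

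**What a correction would buy.** Holm over the 24 unadjusted p-values has a first step at z(1 − .05/48) = 3.078. It gives about 1.4–2.3% false support for Tai Chi. Against the all-pairs reading (1.6–2.7%) the gain is less than half a percentage point.

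**What it would cost.** For a contrast with 80% power at the old threshold c, first-step power is Φ(c + 0.842 − 3.078):
- per visit: Φ(1.960 + 0.842 − 3.078) = Φ(−0.276) = 39%;
- all pairs: Φ(3.031 + 0.842 − 3.078) = Φ(0.795) = 79%.

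**The case for a change.** The best argument for a change is that the same SAP wording permits error rates more than ten-fold apart. The per-visit reading is not far-fetched: the SAP speaks of simple effects at each time point, and each of those compares two means. Dropping the four-contrast reading as non-standard leaves the two extremes, so the ambiguity does not shrink. The remedy looks cheap, too: three sentences and 24 p-values from models already fitted, with no new data.

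Part of this stands. The family is undefined and there is no across-test adjustment. If the per-visit family was used, one isolated significant clinical test is weak evidence for hypothesis 2.

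The rest does not carry a change to the plan. The large figures need two unstated things together: the most permissive support rule and the reading in which the named adjustment does nothing. The hypothesis is worded over the tests collectively, and a consistent pattern across them can be interpreted under any reading. Nor is an isolated result beyond assessment. The six tests and four visits are disclosed, so a reader who has the p-values and knows the family can apply a correction.

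Holm over 24 contrasts would also leave the first gap open. It says which tests pass, not when hypothesis 2 as a whole is supported. A composite, a count rule or a single primary test would be equally defensible. The Protocol is written in the past tense and reports mean attendance of 91% and 94%, so any of these would now be chosen after the fact.

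**Conclusion.** No change to the plan. The documents leave the support rule and the Tukey-Kramer family unstated, but following them as written is not shown to give a wrong result. With all 28 pairs as the family, false support for Tai Chi is about 1.6–2.7% even under the one-test rule, against a nominal 2.5%. Under an all-six rule it is below 1% on every reading. The 19–39% figure arises only if one test at any visit suffices and Tukey-Kramer was applied visit by visit. It also rests on the assumed correlations.

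Replacing the stated method with Holm is a trade-off with no clear winner: negligible gain under one literal reading, and a possible fall from 80% to 39% power for a single contrast under the other. The sensible course is in reporting: state the family used and describe the pattern over all six tests. If the family was per visit, Holm-adjusted p-values can be shown as a post hoc sensitivity analysis, without confirmatory status.

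### Does the SAP need a stated analysis for the falls that the protocol records?

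*Protocol*

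**What the plan says.** The protocol's Objective lists what is measured: "Outcome measures included reactive balance tests involving trip-like perturbations on the modified treadmill, and standard clinical tests of balance and mobility". It then says: "We tested two hypotheses, both of which were motivated by the principle of training specificity". The first hypothesis favours RBT on reactive balance; the second favours Tai Chi on the clinical tests. Neither concerns falls.

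Falls enter in the Design section as an extra: "In addition, real-world falls were tracked for the six months after completing the intervention". The Falls assessment paragraph in Methods adds detail: "The number of all-cause falls and trip-induced falls outside of testing and training were recorded over the six months after the intervention", with the window given as "from week 5 to week 28". On ascertainment it says: "Such falls were quantified through telephone calls made every two weeks to each participant". A fall is defined there.

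The SAP specifies a mixed model for changes from baseline in the clinical and reactive balance measures. It applies a Tukey-Kramer adjustment to the between-group contrasts at each time point that serve the hypotheses. It also has one sentence assigning Fisher's Exact Test to categorical variables, without naming any. Falls appear nowhere in it except in the title.

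**The concern.** The study is called "Balance Recovery Training for Fall Prevention in Retirement Communities", and falls are the only outcome collected outside the test setting. A reader will look for a falls result. Two counts per participant are recorded, yet the SAP leaves open:

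- which fall type leads;
- whether falls are summarised as any fall, a count or a rate;
- how participants followed for only part of the window are handled;
- which test is used, and under what error control.

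If those choices are made with the data in view, a nominally significant falls result could be picked from several candidates. The choice of fall type matters in particular, because RBT trains responses to trip-like perturbations and trip-induced falls may behave differently from all falls.

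**Working it through.** **1. Can any SAP sentence cover falls?**

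- *Mixed model.* It analyses change from baseline with baseline performance as a covariate. No baseline fall count is described, so as written it cannot take falls.
- *Tukey-Kramer.* It is tied to contrasts that address the hypotheses. Falls are in neither, so it does not apply.
- *Fisher's Exact Test.* It names no variable. Faller yes/no is categorical and could be what is meant, but the protocol records numbers of falls and defines no faller category. The sentence is ambiguous: it neither includes nor excludes falls.

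The omission is therefore confirmed, except that a comparison by Fisher's test cannot be ruled out.

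**2. Does the gap reach the hypothesis tests?** No. The named outcome measures and both hypotheses concern reactive balance and clinical tests, and the SAP gives those a model, covariates and an adjustment. None of these uses falls data.

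**3. Is the follow-up window inconsistent?** Weeks 5 to 28 inclusive are 28 - 5 + 1 = 24 weeks, or 24 x 7 = 168 days, with 24 / 2 = 12 scheduled calls. Six calendar months are about 182.6 days. The ratios are 182.6 / 168 = 1.087 and 168 / 182.6 = 0.920, a difference of 8-9%. It would matter only if counts from one window were divided by the length of the other. A rate ratio is unchanged when both arms use the same window. Four weeks of intervention followed by 24 weeks of calls is ordinary rounding of six months.

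**4. How much could free choice matter?** The documents give no sample size, fall rate, dispersion, attrition or trip share, so every input is an assumption:

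| Input | Assumed values |
|---|---|
| Participants per arm | 35, 50, 100 |
| Falls per person | 0.5, 1.0 |
| Dispersion | 0.5, 1.0 |
| Part-followed, both arms | 15% |
| Trip-induced share (no true difference) | 25%, 50% |

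The assumed menu is 2 fall types x 3 summaries (any fall by Fisher's test, count by rank-sum, rate by negative binomial with a log-time offset) x 2 follow-up rules (everyone, fully followed only) = 12 analyses. Simulated with no true difference, two-sided .05, 3000 runs per setting:

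| Analyses available | Chance at least one p <= .05 |
|---|---|
| All 12 | 13-18% |
| 6, all-cause falls only | 8-12% |
| 1 stated all-cause rate analysis | 4.6-6.2% |

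The second and third rows are the like-for-like contrast, since both concern all-cause falls. The upper rows are ceilings that assume free choice.

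**5. What would a faller yes/no summary lose?** With mean m and dispersion k under full follow-up, P(any fall) = 1 - (1 + km)^(-1/k), and the share of falls that are repeats is 1 - P(any fall)/m.

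- m = 0.5, k = 0.5: P = 1 - 1.25^(-2) = 0.36; share = 1 - 0.36/0.5 = 28%.
- m = 1, k = 1: P = 1 - 2^(-1) = 0.5; share = 1 - 0.5/1 = 50%.

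That would be a loss of information in an additional outcome. It would not make the comparison invalid.

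**The case for a change.** The strongest case for acting is that a falls comparison will be read as a result whatever its formal status. Tai Chi was chosen as control partly on evidence that it lowers fall risk, participants were telephoned for about six months, and a few sentences in the SAP would settle the matter with data already collected.

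Part of this stands: the SAP is silent, and a falls p-value from this trial carries no error control. Three things weaken the case for a change.

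- No falls claim is planned, and nothing in the documents shows that an analysis was selected after the fact.
- Writing down an analysis may no longer amount to pre-specification. Both documents carry an October 2015 date, yet the text is in the past tense, the protocol reports that mean "attendance was 91% and 94%, respectively", and its reference list includes a 2017 review. What remains is a matter of labelling and full reporting.
- No single analysis follows from the documents. All-cause falls could lead, but the training-specificity rationale could equally favour trip-induced falls. Adjusting for observed time also presumes that completed and missed calls were logged, which the protocol does not say.

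The lack of a stated direction for falls is not a defect, since a two-sided comparison needs none.

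**Conclusion.** The SAP does omit a falls summary, a rule for unequal follow-up and a clearly identified comparison. This is a gap in detail that analysts fill sensibly, for example with a fall rate over observed time or a comparison of fallers, reported as exploratory. It makes no stated rule wrong and leaves both hypothesis tests as they are. The illustrative size, 8-12% against 4.6-6.2% for all-cause falls, rests wholly on assumed inputs and an assumed menu of analyses. It shows why a falls p-value from this trial should be read with caution; it does not measure an error in this trial. No change to the plan is called for.

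### Does a falls window of week 5 to week 28 contradict the stated six months of follow-up, and does it wrongly leave out the training weeks?

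*Protocol*

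**What the plan says.** The Protocol gives the falls window twice. The Design section says that "real-world falls were tracked for the six months after completing the intervention". The Falls assessment paragraph under Methods repeats the six months and adds week numbers: falls "were recorded over the six months after the intervention (from week 5 to week 28"). The Interventions paragraph sets the length of training as "twelve 30-minute sessions, scheduled three times per week for four weeks", which places training in weeks 1 to 4 and makes week 5 the first week after it.

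Ascertainment is by telephone: "Such falls were quantified through telephone calls made every two weeks to each participant". The quantity recorded is a count: "The number of all-cause falls and trip-induced falls outside of testing and training were recorded".

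The balance tests are also timed in months: "Repeated posttests were conducted one week, one month, three months, and six months after completing the intervention". No week number is given for any posttest, and neither document defines a month.

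The SAP does not name falls. The one sentence that could apply to a faller/non-faller variable is "Differences in categorical variables between groups were evaluated using Fisher's Exact Test".

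**The concern.** Six months and weeks 5 to 28 do not describe the same period if a month is a calendar month. Six calendar months after week 4 end at about week 30. On that reading the stated duration is wrong, fall surveillance closes about two weeks before the six-month posttest, and it is unclear whether a fall in week 29 or 30 counts. A fall rate using six months as its denominator would be too low.

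The second part of the concern is the start of the window. It opens only after training, and the documents describe no recording of falls in weeks 1 to 4. If falls in those weeks went uncounted, any harm from either programme would be missed. Participants who stopped early might also have no clear start of follow-up, so that the falls comparison would no longer be between the groups as allocated. In a study about preventing falls, both points deserve a check.

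**Working it through.** **Inputs.** Training lasts 4 weeks (Protocol, Interventions). The window is weeks 5 to 28, called six months, with a call every 2 weeks (Protocol, Falls assessment). One calendar half-year is 365.25 / 2 = 182.6 days, or 182.6 / 7 = 26.09 weeks.

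**Length of the printed window.** 28 − 5 + 1 = 24 weeks = 168 days, covered by 24 / 2 = 12 calls.

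**Reproducing the plan's figure.**

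| Meaning of six months | Weeks | Ends at week | Matches week 28? |
|---|---|---|---|
| Six months of 4 weeks | 6 × 4 = 24 | 4 + 24 = 28 | Yes, exactly |
| 26 weeks | 26 | 4 + 26 = 30 | No |
| Six calendar months | 26.09 | 4 + 26.09 = 30.1 | No |

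The plan's figure is reproduced with four-week months and with neither of the other two readings.

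**Size of the gap on calendar months.** 26.09 − 24 = 2.09 weeks (14.6 days). As a share of six calendar months this is 2.09 / 26.09 = 8.0%. Taken the other way, six calendar months exceed the window by 26.09 / 24 − 1 = 8.7%.

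**Effect on an absolute rate.** If a count were divided by 0.5 year when the true exposure was 168 / 365.25 = 0.46 year, the rate would be multiplied by 24 / 26.09 = 0.92.

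**Effect on the comparison.** With counts a and b and a common window T, equal numbers per arm for simplicity, the rate ratio is (a/T) / (b/T) = a/b, and T cancels. Fisher's test on the proportion of fallers uses the counts of fallers and non-fallers in that window. It does not use T at all.

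**Posttest timing.** With four-week months the six-month posttest is at 4 + 24 = week 28, when surveillance closes. The two-week gap appears only if calendar months are used for the posttest while the printed weeks are used for falls. The documents give no reason to mix the two.

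**Training weeks.** Weeks 1 to 4 are 4 / 28 = 14% of weeks 1 to 28. Both Protocol statements of the falls outcome place it after the intervention, so excluding these weeks follows the definition and is not a counting error.

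**The case for a change.** The best case for acting has four parts.

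- **Undefined month.** The Design section uses months without weeks for both falls and posttests, so a reader of that section alone cannot tell where week 28 stands relative to the last posttest. This is true, and one phrase would settle it. But the Falls assessment paragraph gives the exact weeks, and no analysis changes with the label.

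- **Start of follow-up.** The Design section ties tracking to finishing the programme, while the Falls assessment paragraph ties it to week 5. The two coincide only for people who finish in four weeks. Mean attendance was 91% and 94%, so some sessions were missed, and the text does not say whether they could be made up later. Falls during training are also expressly excluded, which would be needless if the window always opened after training. This is a real gap, but it is one that an analyst fills from the dates on file. Week 5 can be read as a fixed point on the training calendar for everyone.

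- **Falls during training.** Participants are aged 70 and over, and an RBT session has up to 40 perturbations, so falls in those weeks matter for safety. That stands as a reporting question. It does not show that those weeks went unmonitored: the documents are silent, and silence supports neither conclusion.

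- **Comparison as allocated.** A post-training window can depend on who reaches the end of training. However, the calls went to each participant, and no sentence removes those who stopped early. The charge that dropouts leave the comparison therefore has no text behind it.

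Starting the calls at allocation, or running them to week 30, would also require collecting more data. Both documents are in the past tense and the Protocol already reports attendance, so neither step could be taken now.

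**Conclusion.** No change follows. The window is 24 weeks, which is exactly six four-week months and 8.0% short of six calendar months. With the weeks printed beside the phrase, this is loose wording and not a contradiction.

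The harm is conditional on someone reporting an absolute rate per calendar half-year. That rate would be too low by a factor of 0.92 in both arms, and neither document plans one. Falls are tracked in addition to the balance measures, and neither of the two stated hypotheses concerns them.

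Leaving out weeks 1 to 4 is a consistent choice of outcome: falls once training is over. Counting from allocation is a reasonable alternative but a different estimand.

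This conclusion rests on three assumptions: that week 1 is the first training week, that the same window was applied in both arms, and that the authors used one meaning of month throughout. The first follows from the four-week programme and the week-5 start. The second is how the Protocol describes it. The third is not stated, but it is the only one of the meanings checked that reproduces week 28.
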